## **10.0 Statistical Considerations**

### ***a. Sample size***

The primary outcome will be the change in blood pressure during hemodialysis. For this, we will average blood pressure during hemodialysis of three hemodialysis sessions within the second week of treatment. Secondary endpoints will also be recorded during the second week of treatment and will include the number of hypotensive events, frequency of nursing interventions, average of dialysis recovery times, and average symptoms severity score. Based on our preliminary studies with icatibant and assuming a standard deviation of differences of 13.6 mmHg (pooled SD of the delta), a sample size of 16 in each arm will have 80% power to detect a difference in means of -13.7 mmHg, using a paired t-test with a 0.05 two-sided significance level.

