## 2.0 Rationale and Specific Aims

### A. Specific Aims

In **Specific Aim 1** we will test the hypothesis that **in patients with DIH, inhibition of plasma kallikrein system with lanadelumab prevents the reduction of blood pressure and maintains hemodynamic stability**. For this purpose, we will monitor heart rate and blood pressure during hemodialysis. Importantly, we will conduct the study in an outpatient clinic, using the patients' usual hemodialysis dose and settings as for a regular hemodialysis session. This approach will minimize the risk that our findings were biased by conducting the study in a clinical research setting.

In **Specific Aim 2** we will test the hypothesis that **in patients with DIH, inhibition of plasma kallikrein system with lanadelumab prevents symptoms associated with DIH such as cramps, dizziness, and nausea and improve recovery time after hemodialysis**. Hemodialysis is associated with many complications, including DIH, that negatively affect the QOL of patients and their families. Any intervention that prevents the occurrence of DIH will result in a faster recovery from hemodialysis. The present study will evaluate the impact of lanadelumab on preventing symptoms associated with DIH and reducing recovery time after hemodialysis.

**Figure 3.** Effect of one- week treatment with ramipril or placebo on bradykinin concentrations in response to hemodialysis

[figure not shown]

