## **5.0 Enrollment/Randomization**

This is a parallel study where participants will be assigned to either taking the study drug (lanadelumab) or taking the placebo (saline pre-filled syringes.) Patients will be randomly assigned to the treatment order using a permuted-block randomization algorithm. The study drug, lanadelumab, will be shipped from Takeda as pre-filled syringes along with matching placebo, also in prefilled syringes. The Vanderbilt Investigational Drug Services (IDS) will be responsible for the storage, preparation, dispensing, and labeling of the investigational agents. The Vanderbilt IDS will also maintain accurate drug storage and dispensing logs. Subjects will be randomized to receive a placebo or 300 mg of lanadelumab (Takeda Pharmaceutical, Cambridge, MA). Subjects randomized who do

not complete the whole protocol for any reason will be replaced, and their data will be analyzed separately. The half-life of lanadelumab is 14 days, and the time to reach maximum concentration is five days. For this reason, we will monitor blood pressure and the occurrence of DIH for three weeks after the administration of the second dose of the study drug.

[figure not shown]

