## 6.0 Study Procedures

### Study protocol

After obtaining consent, study subjects will undergo the following procedures.

**COVID-19 precautions prior to and during visits.** Pre-visit phone call – we will contact the patient before all of their study visits to ask a series of COVID-19-related screening questions. Depending on their answers, we will continue with the study visit or postpone for another time. The patient will be asked to wear a face covering during all portions of their study visits in which they are in the presence of hospital staff. We will also encourage frequent hand washing and/or provide alcohol-based hand sanitizer.

Subjects will participate in a randomized, parallel-group, double-blind, placebo-controlled study in which they will receive two doses of placebo or 300 mg of lanadelumab subcutaneously. Participants will continue their usual medications throughout the study. One week (Day -7) before the administration of the first dose of the study drug, we will conduct a study visit at the hemodialysis unit. During this visit, we will give the participants a physical activity monitor to be worn for at least 5 consecutive days and will obtain baseline blood samples. During a second study visit at the dialysis unit (Day -1), we would obtain a second baseline blood sample one to three days before the administration of the first dose of the study drug. In this visit, we will also measure

muscle oxygenation using near-infrared spectroscopy (NIRS). Patients will be then asked to come to the Vanderbilt Clinical Research Center (CRC) on a non-dialysis day. During this visit (Day 0), we will obtain a detailed history, perform a physical examination, administer a quality of life (QOL) questionnaire, obtain the dialysis recovery time, and evaluate body composition and physical performance. We will then administer the first dose of the study drug and monitor the appearance of any Type I (immediate) hypersensitivity reaction for two hours before discharging patients from the CRC. We will repeat the same protocol, as outlined for Day 0 and administer the second dose of the study drug two weeks later at the CRC (Day 14).

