The next two consecutive dialysis treatments after each drug administration (days 1 and 3, and days 15 and 17), we will conduct follow-up visits at the dialysis unit to collect information regarding symptoms after discharge from the CRC. During these visits, at the end of every hemodialysis session, we will also inquire, through a standardized questionnaire, about the presence of any symptoms associated with hypotension. This questionnaire will include symptoms such as cramps, dizziness, nausea, and will be scored according to the severity from 0 to 4 (none to severe). We will also collect blood samples at the dialysis unit for pharmacokinetics and special laboratory analysis. During the six-week length of the study, we will monitor the occurrence of DIH episodes and changes in blood pressure in every dialysis session. For this purpose, we will use the dialysis clinic blood pressure monitor logs. We will also conduct two additional visits at the dialysis units (Day 29 and 43) to draw blood, administer the symptomatology questionnaire, and measure blood flow with NIRS. In the final hemodialysis visit (day 43) we will also give the patients an activity monitor that will be collected after five consecutive days of continuous use. During this last visit, we will also administer the QOL questionnaire, obtain the dialysis recovery time, and perform body composition and physical performance tests (except for the six-minute walk test). Details of the study protocol can be found in Figure 5, Tables 1 and 2, and Appendix 1

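### The week holding the primary and four secondary endpoints is not tied to study days or to a dose, and the marked schedule gives no repeated recovery times in either candidate week

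*Combined protocol and SAP*

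**What the plan says.** Section 10.0 a defines the primary outcome as the change in blood pressure during dialysis: "we will average blood pressure during hemodialysis of three hemodialysis sessions within the second week of treatment". It continues: "Secondary endpoints will also be recorded during the second week of treatment". The four endpoints it then lists are the number of hypotensive events, the frequency of nursing interventions, an average of recovery times and an average symptom severity score. The last two are the outcomes of Specific Aim 2, that lanadelumab "prevents symptoms associated with DIH such as cramps, dizziness, and nausea and improve recovery time after hemodialysis".

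Doses are given on Day 0 and Day 14 (Section 6.0, Study protocol). Section 5.0 cites the drug's half-life and time to peak as its grounds for this statement: "we will monitor blood pressure and the occurrence of DIH for three weeks after the administration of the second dose of the study drug".

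On data collection:
- **Blood pressure and hypotensive episodes:** clinic logs at every session (Study protocol), with 15-minute readings on study dialysis days (Hemodynamic measurements).
- **Symptoms, Study protocol:** for the visits on Days 1, 3, 15 and 17, "During these visits, at the end of every hemodialysis session, we will also inquire, through a standardized questionnaire".
- **Symptoms, Symptoms questionnaire section:** the form is given at the following regular session.
- **Recovery time:** the Dialysis Recovery Time section allows a phone call or the next session and names no days.
- **Appendix A:** recovery time on Days 0, 14 and 43; symptom forms on Days 1, 3, 15, 17, 29 and 43.

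**The concern.** A week of treatment has no unique meaning when two doses are given two weeks apart. Counted from dose 1, the second week ends at about the time of dose 2. Counted from dose 2, it is the week after both doses. These are different questions, and the plan does not say which one the primary analysis answers.

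For blood pressure this is a matter of definition, because the data exist either way. For recovery time and symptoms it is also a matter of collection. A patient's answer that was not obtained at the time cannot be rebuilt from clinic logs. If the schedule is followed as marked, one Aim 2 endpoint lacks the repeated values that its definition calls for, and the other is available for only some of the sessions.

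**Working it through.** The plan gives no figure for this point. Its sample size of 16 per arm does not depend on which week is meant and is used only to cost the fix. The check sets the schedule against the two readings.

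**1. Dialysis sessions.** Appendix A's dialysis days -1, 1, 3, 13, 15, 17, 29 and 43 leave remainders 6, 1, 3, 6, 1, 3, 1 and 1 on division by 7 (Day -7 appears to carry a tolerance of 3 days and is left out). They fit one thrice-weekly calendar: Days 1, 3, 6, 8, 10, 13, 15, 17, 20 and so on. A second calendar, Days 1, 3, 5, 8, 10, 12, 15, 17, 19, also fits Section 6.0, since the visit before dosing may fall one to three days ahead. It misses only nominal Day 13.

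**2. Candidate windows.** Days 7–13 or 8–14 (from dose 1), and Days 14–20 or 15–21 (from dose 2).

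**3. Order on Day 14.** The Day 0 description lists recovery time among the assessments and then says "We will then administer the first dose of the study drug". For Day 14: "We will repeat the same protocol, as outlined for Day 0 and administer the second dose of the study drug two weeks later". So the Day 14 recovery time precedes dose 2 and describes earlier sessions.

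**4. Counts.**

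| | Second week after dose 1 | Week after dose 2 |
|---|---|---|
| Sessions, first calendar | 8, 10, 13 | 15, 17, 20 |
| Sessions, second calendar | 8, 10, 12 | 15, 17, 19 |
| Sessions after a Day 14 dose | 0 of 3 | 3 of 3 |
| Recovery times marked | 0 (Days 7–13) or 1 (Days 8–14) | 1 (Days 14–20) or 0 (Days 15–21) |
| Of these, taken after dose 2 | 0 | 0 |
| Symptom forms marked | 0; 1 if Table 1 covers Day 13 | 2 |
| Window sessions described, form about the same session | 0 of 3; 1 if Table 1 covers Day 13 | 2 of 3 |
| Window sessions described, form about the previous session | 1 of 3 (from the Day 15 form); 2 if Table 1 covers Day 13 | 1 of 3 |
| Window sessions that are study dialysis visits | 0 or 1 of 3 | 2 of 3 |

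The entries that turn on Day 13 arise because Appendix A marks it as a dialysis visit but not for symptoms or the blood pressure log, Section 6.0 does not describe it, and Table 1 lists the questionnaire without restricting days. If a form describes the previous session, the Day 15 form describes a session before dose 2.

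**5. Tolerance.** Appendix A prints a tolerance of 4 days, apparently above Day 14; its span cannot be read with certainty. On the first calendar, a second dose on Day 11 or 12 would put one of the three earlier sessions (Day 13) after it. Nominal days therefore cannot define the window for every patient.

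**6. Blood pressure model.** Section 10.0 b models readings taken every 15 minutes. At least one session in either window is not a study visit, so its readings come from clinic logs, whose interval is not stated.

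**The case against.** The strongest reply has four parts.

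- **An average is still possible.** Section 10.0 a does not say that the averages are per patient. One recovery time per patient gives an arm mean, and Days 14–20 hold one recovery time and two symptom forms. This stands: a reader might infer that no average recovery time can be computed at all, and that is too strong. What cannot be formed is a patient's average over sessions. The one value available also precedes dose 2, so it cannot describe the week after it.
- **The text is more generous than the table.** Recovery time may be asked by phone or at the next session. True, but no day is named and no such contact is marked in either week.
- **The recovery question is general.** It asks how long recovery from a session takes and names no session. If it captures usual recovery, one answer is not a one-session measurement. This stands, and it is why no loss of precision is claimed here.
- **The calendar is nominal, and Figure 5 may settle the matter.** Both stand as limits. On either calendar, however, the two windows share no session and the counts of marked assessments are the same.

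A reader might also infer that the primary outcome cannot be obtained, that a one-dose window is a mistake, or that the type I error is inflated. The documents support none of these. Logs cover every session; a one-dose window is a legitimate choice if stated; and the trial is double-blind, with nothing to suggest that the window would be chosen after unblinding.

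**Conclusion.** The point holds in this form: the window is undefined in the visible text, and the marked schedule does not match the two Aim 2 endpoints placed in it.

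- **Primary outcome, hypotensive events, nursing interventions:** obtainable from clinic records on either reading; only the choice of week is open. For nursing interventions this assumes that the clinic records them, since the plan names no source. The post-dose-2 monitoring in Section 5.0 does not settle the choice, because it spans three weeks rather than one.
- **Recovery time:** at most one marked value in either week, and none taken after dose 2 until Day 43.
- **Symptoms:** no marked form in the earlier week (one if Table 1 covers Day 13) and two in the later week. Those two describe two of the three sessions after dose 2, or only one if the form refers to the previous session.

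This rests on reading Appendix A by column position, on dose 2 at nominal Day 14, and on Figure 5 not defining the week. It should be fixed, but it does not make the primary outcome unanalysable.

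**What to change.** Before unblinding:

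1. In Section 10.0 a, define the window by session number counted from an actual dose date, not by nominal days. If the effect after both doses is the target, the first three sessions after dose 2 would serve. If a one-dose window is meant, say so and schedule the assessments there.
2. Reconcile the Study protocol, Dialysis Recovery Time and Symptoms questionnaire sections, Section 10.0 a and Appendix A (with Table 1 for Day 13). Schedule the symptom form and the recovery question for each session in the window, and have each form record the session it describes.
3. In Section 10.0 b, state the log interval and how log readings enter the 15-minute model for sessions that are not study visits.
4. A window counted from dose 2 does not exist for a patient who never receives it. State how such patients enter the analysis, consistently with Section 5.0 (non-completers replaced and analysed separately) and with Sections 8.0 and 9.0 (withdrawal before dose 2).

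**Cost.** Wording, plus about two short contacts per patient. With a window after dose 2 and questions asked at the next session, the first session is covered at the existing Day 17 visit. The other two are asked about at the following two regular sessions (nominally Days 20 and 22) or by phone: 2 × (16 + 16) = 64 contacts before replacements. Added symptom forms can use the same contacts. Taking 15-minute readings at the third session, if preferred to logs, adds one session per patient, 32 in all. Asking about specific sessions narrows the general wording of the recovery question, and the plan should say so.

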### ***b. Data analysis plan***

Standard graphing and screening techniques will be used to detect outliers and to ensure data accuracy. Distributions of the continuous outcomes will be assessed for normality. If normality is violated, proper data transformation will be applied, or non-parametric analysis methods will be considered. The primary endpoints are SBP and DBP. The secondary endpoints include heart rate, and the R-R interval (autonomic function), the time to recover after HD, symptoms associated with DIH, and the distance walked during the six-minute walk test.

Mixed effect models will be used to analyze the primary endpoint (blood pressure) with a random subject effect and with the treatment (lanadelumab vs placebo) and the time trend (measurements every 15 minutes) as fixed effects. The focus of this study will be the treatment effect and the time trend of the endpoints; however, mixed effect models also provide the flexibility of controlling for and evaluating covariates. However, we will be careful not to over-fitting the model due to the limited sample size.

Besides the above evaluation of the treatment effect and the time trend through the regression models, the direct treatment effect will also be estimated as within-subject mean difference along with their 95% confidence intervals. For the secondary endpoints, a paired t-test will be performed (lanadelumab vs placebo). If the normality of the data is violated, we will use non-parametric tests.

For binary endpoints (e.g., occurrence of hypotensive events), we will use the McNemar test to compare lanadelumab and placebo.

**Missing Data.** Based on our previous studies, we anticipate a drop-out rate of 10% or less. Subjects who drop out will be replaced. Specific inferences on effects of interest will be made by reporting a point estimate along with a 95% confidence interval and the p-value. Hypotheses will be tested at the level of  $\alpha=0.05$ . We will use SPSS (version 25.0, SPSS, Chicago, IL) and the open-source statistical package R (R Core Team, 2017) for analyses.

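### Two primary endpoints, SBP and DBP, are named at 0.05 with no success rule, while the sample size covers one unnamed blood pressure

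*Combined protocol and SAP*

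**What the plan says.** Section 10.0 of the combined protocol and SAP describes the primary endpoint in three ways.

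- Section 10.0 a has one outcome, with no pressure named: "The primary outcome will be the change in blood pressure during hemodialysis". The sample size of 16 per arm is said to give "80% power to detect a difference in means of -13.7 mmHg", with an SD of 13.6 mmHg, "using a paired t-test with a 0.05 two-sided significance level".
- Section 10.0 b has two: "The primary endpoints are SBP and DBP".
- The model paragraph of section 10.0 b returns to the singular: "Mixed effect models will be used to analyze the primary endpoint (blood pressure", again without choosing a pressure. It adds: "The focus of this study will be the treatment effect and the time trend of the endpoints".

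The error rate is given once for all tests: "Hypotheses will be tested at the level of" 0.05. Specific Aim 1 in section 2.0 speaks only of blood pressure, so it does not settle the matter. No section gives a hierarchy, an alpha split, a multiplicity adjustment, or a rule on whether one or both pressures must be significant.

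**The concern.** The trial may end with a significant SBP result and a non-significant DBP result, or the reverse. The plan does not say whether Aim 1 has then succeeded, so the decision would be made after the data are seen.

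The two natural rules have different consequences. If either pressure suffices, two chances at 0.05 push the overall false positive rate above the stated level. If both are required, the error rate is safe, but the stated power describes only one of the two hurdles. The sample size section cannot show which rule was meant, because it does not name the pressure it powers.

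**Working it through.** **Inputs from section 10.0 a:** difference 13.7 mmHg in absolute value, SD 13.6 mmHg, 16 per arm, two-sided 0.05, stated power 80%. **From section 10.0 b:** two primary endpoints, tests at 0.05. **Not in the documents:** the SBP–DBP correlation, and any effect or SD identified as diastolic.

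**1. Reproduce the planned sample size.** Section 5.0 describes parallel groups ("This is a parallel study where participants will be assigned to either taking the study drug (lanadelumab) or taking the placebo"), so the comparison is between two independent arms.

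- Standardised effect: d = 13.7 / 13.6 = 1.007.
- Normal approximation: n per arm = 2 × (1.960 + 0.842)² / 1.007² = 15.5, rounded up to 16. This matches the plan.
- Two-sample t-test with 16 per arm: df = 30, noncentrality = 1.007 × √(16/2) = 2.85, power = 78.7%. With 17 per arm it is 81.3%.

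The stated 16 is thus the size for one endpoint tested once at 0.05. The paired test named in section 10.0 a does not suit this design; that is a separate matter, and no result below uses it.

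**2. If either pressure counts.** Assume one treatment test per pressure, jointly normal test statistics with correlation ρ, and no true effect on either pressure. Then

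P(at least one significant) = 1 − P(|Z₁| < 1.96 and |Z₂| < 1.96).

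At ρ = 0 this is 1 − 0.95² = 0.0975. At other values it comes from the bivariate normal distribution:

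| Assumed ρ | False positive chance, either counts |
|---|---|
| 0 | 9.75% |
| 0.5 | 9.1% |
| 0.7 | 8.3% |
| 0.8 | 7.8% |
| 0.9 | 7.0% |
| 0.95 | 6.5% |

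Simulated two-sample t-tests with 16 per arm (400,000 runs per value) gave 9.7%, 9.1%, 7.8% and 6.6% at ρ = 0, 0.5, 0.8 and 0.95, so the normal calculation is adequate at this size.

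**3. If both must succeed.** With no effect on either pressure, the chance that both are significant is 0.05 + 0.05 minus the figure in the table. At ρ = 0.8 that is 10% − 7.8% = 2.2%, and at 0.95 it is 10% − 6.5% = 3.5%. If only one pressure is truly affected, a joint win still needs a false positive on the other, so the rate is at most 5%. There is no inflation.

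Joint power cannot exceed the power of either endpoint alone. It is therefore at most 78.7% for the stated effect on a two-sample t-test. How far below that it falls cannot be computed, because planning values exist for one pressure only.

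**The case against.** The strongest reply is that SBP was plainly meant. The definition of dialysis-induced hypotension and the eligibility criterion in section 4.0 are systolic. The icatibant result in section 3.0, from the studies on which section 10.0 a draws, is described in the text as an SBP effect. Figure 4, which shows that result, is not visible in the text reviewed and may identify the pressure. This makes SBP the likely intention, but the only sentence that names the primary endpoints gives SBP and DBP equal standing, so a reader cannot treat SBP alone as prespecified.

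Second, no section says that a win on either pressure suffices. This stands. A reader might infer from the table that the trial runs an inflated error rate, but the documents support that only conditionally. What holds without any assumed rule is that the success criterion is missing.

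Third, a reader might take 6.5–7.8% as the realistic range because both pressures come from the same cuff readings. A shared device does not establish a correlation of 0.8 or more between patients' changes in the two pressures, and the documents give no value. Nor is 9.75% a firm ceiling on what the plan allows. It assumes jointly normal statistics (without that assumption the bound for two tests is 10%) and one test per pressure, whereas section 10.0 b also makes the time trend a focus.

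Fourth, a reader might conclude that the trial is badly underpowered for a joint claim. That would require invented DBP effects.

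**Conclusion.** The concern holds as an unresolved definition of the primary result. Section 10.0 b names two primary endpoints, section 10.0 a powers one unnamed pressure, and no rule connects them. That rests on the text alone and is firm.

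The numerical consequence is conditional. Under an either-wins rule, with one treatment test per pressure and jointly normal statistics, the false positive chance exceeds 5%, ranging from 6.5% at correlation 0.95 to 9.75% at correlation 0. Under a both-must-win rule the error is controlled and the open question is power, which the documents do not allow anyone to assess. The issue should be corrected before analysis. It does not show that any particular result would be wrong.

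**What to change.** 1. In section 10.0 b, replace the sentence naming two primary endpoints with wording such as: *The single primary test is the lanadelumab-versus-placebo effect on the change in SBP during hemodialysis, at two-sided 0.05. DBP is tested at two-sided 0.05 only if SBP is significant.*
2. Name SBP in the model sentence of section 10.0 b and wherever section 10.0 a refers to blood pressure as the outcome.
3. In section 10.0 a, state that the −13.7 and 13.6 mmHg figures are systolic, or give the systolic figures and restate the power. With the current figures, a two-sample t-test at 16 per arm gives 78.7%.

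This order of testing holds the error for the two pressures at 5% and costs SBP no power. By comparison, splitting alpha at 0.025 each would cut power for the stated effect to 68.7% at 16 per arm. The time trend can stay in the model as planned, provided the treatment effect on SBP is stated as the primary test.

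The cost is a few wording edits, with no change to visits or data collection. The multiplicity rule itself does not call for more patients, though the power should be restated if the systolic figures differ. The downside is that DBP alone can no longer carry the primary claim.

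### SBP and DBP are both primary at 0.05 with no success rule, and the primary model states neither its response scale nor a baseline, although the trial was sized as one test on a change in BP

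*Combined protocol and SAP*

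**What the plan says.** **Sizing (section 10.0 a).** "The primary outcome will be the change in blood pressure during hemodialysis". SBP or DBP is not specified. The next sentence averages intradialytic BP over three sessions in the second week of treatment and mentions no subtraction of a starting value. The calculation is made "assuming a standard deviation of differences of 13.6 mmHg (pooled SD of the delta"), for a difference of -13.7 mmHg, 16 per arm and 80% power, "using a paired t-test with a 0.05 two-sided significance level".

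**Analysis (section 10.0 b).** "The primary endpoints are SBP and DBP". BP is analysed by a mixed model "with a random subject effect and with the treatment (lanadelumab vs placebo) and the time trend (measurements every 15 minutes) as fixed effects". Of covariates the plan says only that "mixed effect models also provide the flexibility of controlling for and evaluating covariates"; none is named. It adds that "the direct treatment effect will also be estimated as within-subject mean difference", with a 95% confidence interval. All hypotheses are tested at 0.05. No hierarchy, alpha split or both-required rule is given.

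**Design and measurement.** Section 5.0 describes a parallel trial, so each patient receives only one treatment. Section 6.0 (Hemodynamic measurements) defines a baseline BP as the mean of three readings in the 15 minutes before dialysis. Section 10.0 does not refer to it. Section 4.0 defines dialysis-induced hypotension (DIH) by a fall in systolic pressure.

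**The concern.** Three parts of the primary analysis do not fit together.

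- **Number of endpoints.** The sample size was built for one test. Two primaries at the full 0.05 either raise the false-positive rate (if one is enough) or lower the power (if both are needed). The plan does not choose, so the choice could be made after the data are seen.
- **Scale and baseline.** The sized quantity is a change. The model names BP as its response, leaves the scale open and omits the baseline. If the response is raw BP, the treatment term is the arm difference in mean intradialytic level. Randomisation makes that unbiased, but it carries the between-patient spread in pre-dialysis BP and is not the quantity that was sized.
- **Pairing.** A paired t-test and a within-subject treatment difference need both treatments in the same patient. Here a within-subject difference can only be a change over time within one arm.

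With 16 patients per arm, any of these choices could alter the reported result.

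**Working it through.** **1. Reproduce the stated size.** Inputs from section 10.0 a: difference 13.7, SD 13.6, n = 16 per arm, two-sided 0.05.

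- Normal approximation, two samples: n = 2 × (1.960 + 0.842)² × (13.6/13.7)² = 15.47, rounded up to 16 per arm.
- Exact two-sample t: noncentrality = 13.7 / (13.6 × √(2/16)) = 13.7/4.808 = 2.849; 30 df; critical value 2.042; power **78.7%**. With 17 per arm it is 81.3%.
- Paired t as stated, 16 pairs: noncentrality = 13.7 / (13.6/√16) = 13.7/3.4 = 4.029; 15 df; power **96.4%**. Ten pairs would already give 80.9%.

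So 16 per arm fits one unpaired comparison at the full 0.05. That is an inference from the arithmetic; the text says paired.

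**2. Two primary endpoints at 0.05 each.** The SBP-DBP test correlation ρ is not in the documents; 0.5 and 0.8 are assumed. No DBP effect or SD is given, so DBP is assumed to have the same 78.7% power. Test statistics are taken as bivariate normal with shift 1.960 + 0.797 = 2.757 under the alternative, where 0.797 is the normal quantile of 0.787.

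| ρ | Either wins: P(at least one \|Z\| > 1.96) under the null | Both must win: P(both Z > 1.96) under the alternative |
|---|---|---|
| 0.5 | 9.1% | 67% |
| 0.8 | 7.8% | 71% |

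**3. Does level instead of change cost power?** The documents give no SD for pre-dialysis or intradialytic SBP. For illustration, read 13.6 as the SD of mean intradialytic minus pre-dialysis SBP, and assume both have the same SD, s. The level comparison then uses s in place of 13.6 (16 per arm, 30 df):

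| Assumed s (mmHg) | Power on level | Power on change |
|---|---|---|
| 10 | 96% | 78.7% |
| 13.6 | 78.7% | 78.7% |
| 17.3 | 58% | 78.7% |

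The value 17.3 is the SD of a uniform spread over the eligible range: (170 - 110)/√12. The sign of the difference changes within a plausible range, so the documents cannot settle it.

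**4. What adjustment does.** Let B be the session's pre-dialysis SBP and Y the intradialytic SBP. If Y = a + τ·treatment + γ·B + other terms, then Y - B = a + τ·treatment + (γ - 1)·B + the same other terms. The treatment effect τ is identical, so the question of level or change disappears. If r is the correlation between B and the change, the residual SD is 13.6 × √(1 - r²). Under the equal-SD assumption r = -13.6/(2s), so:

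- s = 10: r = -0.68, residual SD 9.97, power 96%.
- s = 13.6: r = -0.50, residual SD 11.78, power 89%.
- s = 17.3: r = -0.39, residual SD 12.51, power 85%.

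Without the equal-SD assumption, the least favourable case is r = 0: the residual SD stays at 13.6 and only one df is lost (29 df, power about 78.6%). Simulated trials over a wider grid of assumed SDs and r gave 77-96%.

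**The case against.** The strongest reply is that the plan can be read coherently. Section 10.0 b assigns the mixed model to the primary endpoint, and section 10.0 a has defined that endpoint as a change, so the response may be the change. Covariates are permitted. The within-subject difference is introduced as an addition to the model, so the treatment term is the natural deciding result. The unadjusted comparison is unbiased in any case.

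Much of this stands, and it rules out several stronger readings:

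- *The model definitely analyses level while the sizing uses change.* The text does not say so. The blur already sits inside section 10.0 a, where an outcome called a change is followed by a plain average.
- *No estimate leads.* The treatment term is the leading candidate. "The focus of this study will be the treatment effect and the time trend of the endpoints" might suggest a treatment-by-time test, but no such term is listed, and a time main effect compares no arms.
- *Power is lost by analysing level.* Step 3 of the working shows that the direction depends on SDs the documents do not give.
- *The analyst will try level, change and adjusted BP and claim any win.* The plan does not offer these as alternatives, so an error rate calculated on that basis would describe assumed behaviour, not the plan.

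The reply does not supply a success rule for SBP and DBP, a stated response scale or a named baseline covariate. Nor does it make a paired test fit a parallel design. An adjustment that is merely allowed is not prespecified.

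**Conclusion.** The concern holds in this form. The plan sizes one test of a change in BP and then names two primary endpoints at 0.05 with no success rule. The consequence is a familywise error of about 7.8-9.1% if either can win, or power of about 67-71% if both must. These figures rest on the assumed correlation and, for the power, on DBP being as well powered as SBP.

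A reader might infer that the error rate is certainly inflated. It is inflated only under an either-wins rule; the fault is that no rule is given.

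The unstated response scale and the unused baseline are real gaps, but the documents show neither bias nor a definite loss of power from them. The paired wording is wrong for this design: the stated n corresponds to an unpaired test with 78.7% power, slightly below the 80% claimed. The sizing figures need no outside assumption. The points should be settled before unblinding, because a prespecified test cannot be restored afterwards.

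**What to change.** 1. Name SBP as the single primary endpoint, since the plan defines DIH on SBP, and make DBP secondary.
2. Name one deciding result: the treatment term of the planned mixed model for intradialytic SBP over the three primary-week sessions, with the session's pre-dialysis SBP (section 6.0, Hemodynamic measurements) added as a covariate. Note that this value follows the first dose, so the estimate describes SBP during dialysis at a given pre-dialysis SBP and would not capture any drug effect on pre-dialysis SBP itself. The three-reading baseline is planned for study days, so say which reading serves in any primary-week session that is not a study visit.
3. Restate the within-subject difference as the between-arm difference in change, supportive only, and the sizing as a two-sample t-test with 78.7% power at 16 per arm.

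**Cost.** SAP wording, one of the 30 degrees of freedom (16 + 16 - 2), DBP's primary status, and a stated power slightly below 80%. The main change needs no additional patients.
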